5.6 Women of Childbearing Potential

Women of childbearing potential (WOCBP) includes any female who has experienced menarche and who has not undergone successful surgical sterilization (hysterectomy, bilateral tubal ligation, or bilateral oophorectomy) or is not postmenopausal. Essure, tubal occlusion and endometrial ablation are not acceptable methods of contraception. Menopause is defined as:

- Amenorrhea greater than or equal to 12 consecutive months without another cause and a documented serum follicle stimulating hormone (FSH) level > 35mIU/mL

NOTE: FSH level testing is not required for women greater than or equal to 62 years old with amenorrhea of greater than or equal to 1 year

or

- Woman on hormone replacement therapy (HRT) who no longer menstruate.

Women of childbearing potential (WOCBP) and all men must understand the following requirements and use an acceptable method of contraception to avoid pregnancy throughout the study and for up to 90 days after the last dose of investigational product in such a manner that risk of pregnancy is minimized.

The requisite drug interaction studies to determine the interaction of zavegepant with oral contraceptives have not been performed to date. It is, therefore, not possible to determine the efficacy of oral contraceptives as an effective method of contraception for WOCBP or men with partners who are WOCBP who are participating this study. Oral estrogen and progestin hormonal contraceptives as a sole method of contraception are therefore prohibited.

It is required that all WOCBP use 2 methods of contraception to prevent pregnancy, for the duration of the study (i.e. this study begins with signed consent form through 90 days after dosing with study drug). The 2 methods should include 1 barrier method (ex. condom with spermicidal gel, non-hormonal intrauterine devices, cervical cap etc.) and 1 other method. The other method could include hormonal contraceptives (e.g. oral contraceptives, injectable contraceptives, patch, or contraceptive implant [e.g. hormonal intrauterine device]) used since at least 4 weeks prior to sexual intercourse or another barrier method.

WOCBP and all male subjects must be counseled on the requirements to avoid pregnancy throughout the study and for 90 days after the last dose of study medication, as well as acceptable methods of contraception to use during the study. Subjects who report abstinence, or who report exclusively being in same-sex relationships are still required to understand the contraception requirements in this study to prevent pregnancy. If subjects who report abstinence, or who report exclusively being in a same-sex relationship engage in heterosexual activity, then the contraception requirements must be followed.

Males with vasectomy are considered surgically sterile provided the procedure occurred greater than 6 months (24) weeks prior to the screening visit. Vasectomy is considered one form of contraception; therefore, one additional form of contraception must be used to fulfill the contraception requirements for the study. Male subjects must not donate sperm until 90 days following the last study drug administration.

All WOCBP must complete the pregnancy test schedule [Table 1](#).

Women who suspect that they have become or may have become pregnant despite using proper birth control methods, should use the home pregnancy test provided at Baseline Visit. All WOCBP must administer the home pregnancy test prior to taking investigational study drug. If the pregnancy test is positive, subjects should not take study drug and should immediately contact the Investigator.

5.7 Other Restrictions and Precautions (if applicable)

Not Applicable.

5.8 Deviation from Inclusion/Exclusion Criteria

Any significant event that does not comply with the inclusion criteria, exclusion criteria, study conduct, or study procedures will be documented as a deviation. Deviations will be documented and reported through the clinical monitoring of the trial. Deviations will be reported to the IRB/EC at the frequency required by your IRB/EC. Prospective approval of protocol deviations to recruitment and enrollment criteria, also known as protocol waivers or exemptions, is not permitted.

6 STUDY CONDUCT AND DESCRIPTION OF STUDY PROCEDURES

6.1 Study Materials

The following study materials will be provided at the study start:

- Investigator File/Study Binder
 - Drug Accountability Logs
 - Sample source documents
 - Concomitant and Rescue Medication Logs (take home for subject)
 - Investigator Brochure
 - Interactive Web-based Response System (IWRS) manual
 - Electronic Case Report Forms (eCRF)
 - Electronic Case Report Forms (eCRFs) will be prepared for all data collection fields
 - eCOA Handheld devices
 - One device to be kept onsite for training purposes with training materials
 - Supply of devices for each randomized subject to receive 1 device to use during the treatment phase
 - Drug administration instructions
 - Laboratory kits and laboratory manual
 - Home pregnancy test for each randomized subject of WOCBP
 - ECG Machine and instructions
 - SAE forms and SAE Reporting instructions
 - Pregnancy surveillance forms
 - S-STS source documents
 - Single use, disposable nasal speculum provided upon request
-

- Study system access:
 - Electronic Data Capture (EDC) tool to submit study data to Sponsor/ CRO
 - IWRS
 - Central Laboratory

6.2 Eligibility Assessments

As outlined in [Table 1](#): Informed consent, inclusion/ exclusion criteria, medical history study procedures, migraine history assessment, concomitant medication paper diary, ECG and randomize subject in IWRS

6.3 Safety Assessments

6.3.1 Vital Signs and Physical Measurements (Height and Weight)

Body weight and height will be recorded at the scheduled visits as outlined in [Table 1](#).

6.3.2 Electrocardiogram (ECG)

A standard 12-lead ECG will be recorded during the Screening Phase and at the scheduled visits as outlined in [Table 1](#). A central ECG service will be utilized for all ECGs and based on the central read, the Investigator will determine if any abnormalities are of clinical significance.

6.3.3 Physical Exam

Subjects will undergo a complete physical examination at the Screening visit and at the scheduled visits as outlined in [Table 1](#). The directed physical exam should be guided by the subject's signs and symptoms. Physical exam will include nasal inspection.

If applicable, Investigators should pay special attention to clinical signs related to previous serious illnesses.

6.3.3.1 Nasal Inspection

The nasal passages and turbinates will be visually inspected by the Investigator or medically qualified delegate with a nasal speculum or otoscope at the Screening, Baseline and EOT Visits (refer to [Table 1](#)) to detect evidence of significant nasal conditions that may affect the administration or absorption of the nasal product (e.g. severe septum deviation, nasal deformity or blockage, inflammation, perforation, mucosal erosion or ulceration, polyposis, nasal trauma). Nasal findings will be recorded as appropriate and followed until resolution.

6.3.4 Laboratory Assessments

The investigator must review all laboratory reports, document this review, and record any clinically relevant changes occurring during the study in the AE section of the CRF (see guidance in Section 8.2.2). The laboratory reports must be filed with the source documents. Clinically significant abnormal laboratory findings are those which are not associated with the underlying disease, unless judged by the investigator to be more severe than expected for the participant's condition.

All laboratory tests with abnormal values considered to be clinically significant during participation in the study should be repeated until the values return to normal or baseline or are no longer considered clinically significant by the investigator or medical monitor.

If such values do not return to normal/baseline within a reasonable period of time as judged by the investigator, the etiology should be identified, and the sponsor notified.

All protocol-required laboratory assessments must be conducted in accordance with the laboratory manual and Table 1.

If laboratory values from non-protocol specified laboratory assessments performed at the institution's local laboratory require a change in study management or are considered clinically significant by the investigator (e.g., SAE or AE or dose modification), then the results must be recorded in the CRF.

6.3.4.1 Safety Laboratory Testing

Blood and urine samples will be obtained as outlined in Table 1 for clinical laboratory evaluations. A central laboratory vendor will be utilized for this study and a laboratory manual will be provided to each site. **If possible, subjects should be fasting for a minimum of 8 hours prior to all blood draws.** However, if a subject is not fasting at a given visit, the blood draw should still be performed, and the non-fasting status should be documented.

Hematology: Hemoglobin, hematocrit, red blood cell count, white blood cell count (WBC) with differential, and platelets.

Blood chemistry/electrolyte: Sodium, potassium, chloride, bicarbonate, calcium; glucose, BUN (urea), serum creatinine, uric acid, ALT, AST, alkaline phosphatase, LDH, total protein, albumin, total bilirubin, direct bilirubin, indirect bilirubin, CK. EOT Visit – elevations in CK (>5x ULN) may have further CK fractionation tests performed.

Lipid panel: Total cholesterol, LDL cholesterol, HDL cholesterol, triglycerides.

Estimated glomerular filtration rate: eGFR using the estimated MDRD formula will be calculated and reported by the central lab at each visit that clinical laboratory tests are collected as outlined in Table 1.

Urinalysis: pH, specific gravity, ketones, nitrites, urobilinogen, leukocyte esterase, protein, glucose and blood. If blood, protein or leukocytes are positive, reflex to microscopic examination.

Urine Drug Screen: For drugs of abuse including but not limited to cocaine, amphetamines, opioids, PCP, THC and barbiturates.

Reflex tests:

- If ALT or AST ≥ 3 x ULN OR total bilirubin ≥ 2 x ULN at any visit after the baseline visit, the central laboratory will perform reflex tests that may include: CK, GGT, and anti-viral serologies. Subjects may have to return to the study site to provide additional blood samples for these laboratory tests.

Additional laboratory tests may be required.

6.3.4.2 *Pregnancy Testing*

Pregnancy tests will be conducted (serum, urine, or home pregnancy test), when appropriate and as outlined in [Table 1](#). If applicable, a FSH test will be obtained at screening to confirm WOCBP status.

6.3.5 ***Sheehan Suicidality Tracking Scale (S-STs)***

The S-STs is a prospective clinician administered rating scale that contains questions that track both treatment-emergent suicidal ideation and behaviors^{13,14}. The S-STs will be completed on a paper form at the site. At the screening visit, the recall period for completing the S-STs is within the last 30 days prior to the screening visit; at all other visits, the recall period for completing the S-STs is since the last visit (reference [Table 1](#)). Subjects who have a S-STs score of >0 should be evaluated by the Investigator. If the Investigator determines that a subject is at risk of suicide or self-harm, appropriate measures to ensure the subject's safety and obtain mental health evaluation must be implemented. In such circumstances, the subject must immediately be discontinued from the study. The event should be recorded as either an AE or SAE as determined by the investigator and reported within 24 hours to the Sponsor.

6.4 **Efficacy Assessments**

6.4.1 ***Pain***

Subjects record their headache pain intensity using a 4-point numeric rating scale (none, mild, moderate, severe) in the eCOA handheld device at the time points indicated in [Table 1](#).

6.4.2 Nausea, Phonophobia and Photophobia

Subjects will record the status (present or absent) of their migraine associated symptoms of photophobia, phonophobia and nausea in the handheld at the time points indicated in [Table 1](#). In addition, subjects will record the intensity of the symptom on a 4-point numeric rating scale (none, mild, moderate, or severe) in the handheld at the same time points.

Subjects will also record their current MBS (nausea, phonophobia or photophobia) in the handheld before taking study drug.

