5.1 Number of Subjects

It is anticipated that approximately 1,750 subjects will need to be screened in order to randomize approximately 1,400 subjects. The subjects will be randomized in a 1:1 ratio to the zavegepant or matching placebo treatment groups. It is anticipated that enrollment will occur at approximately 65 sites in the United States over a period of approximately 5 months during this trial.

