9 STATISTICS

9.1 Sample Size

It is anticipated that about 90% of the 700 subjects randomized to each treatment group will have a headache in the allotted time period, resulting in approximately 630 subjects evaluable for efficacy in each treatment group.

The sample size calculation is based on results from the Phase 2/3 dose-ranging study BHV3500-201. The response rates for the pooled zavegepant 10 mg and 20 mg groups, and for the placebo group in study BHV3500-201 were 22.8% and 15.5%, respectively, for pain freedom at 2 hours postdose, and 42.2% and 33.7%, respectively, for MBS freedom at 2 hours postdose.

A total sample size of 1,260 evaluable subjects (630 per group) will provide approximately 91% power for the co-primary endpoint of pain freedom at 2 hours postdose, approximately 88% power for the co-primary endpoint of MBS freedom at 2 hours postdose, and approximately 80% power to detect a difference between treatment groups for both endpoints jointly.

9.2 Analysis Sets:

- Enrolled: Subjects who sign informed consent and are assigned a subject identification number.
- Randomized: Subjects in the enrolled analysis set who receive a randomized treatment group assignment (zavegepant or placebo) from IWRS.
- Safety: Subjects in the enrolled analysis set who take study drug (zavegepant or placebo).
- Efficacy: Subjects in the randomized analysis set who: (1) are randomized only once; (2) have a migraine of moderate or severe pain intensity at the time of dosing; (3) take study drug; and (4) have postdose efficacy data (i.e., non-missing pain intensity, phonophobia status, photophobia status, nausea status, or functional disability level after taking study drug).

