9.3.1 Efficacy Analyses

The intercurrent event of rescue medication use will be handled using RM=F, i.e., subjects who take rescue medication will be classified as failures for all efficacy assessments that are reported at or after taking rescue medication. The RM=F method will apply to all efficacy endpoints, except the secondary efficacy endpoint of rescue medication use within 24 hours postdose.

9.3.1.1 *Primary Endpoints*

Zavegepant will be tested for superiority against placebo at an $\alpha=0.05$ level for both co-primary endpoints using the efficacy analysis set. For each endpoint, treatment groups will be compared using a Cochran-Mantel Haenszel test to estimate the difference in percentages of subjects achieving the endpoint response criteria (zavegepant – placebo) stratified by prophylactic migraine medication use at randomization (yes or no). The percentage of subjects achieving the endpoint response criteria will be presented with a 95% confidence interval (CI) by treatment group. The difference in percentages between treatment groups will be presented with a 95% CI and p-value.

Subjects with missing data at 2 hours postdose will be classified as failures (i.e., Non-Completer = Failure; NC=F).

Sensitivity analyses will be described in the SAP.

9.3.1.2 *Secondary Endpoints*

If the tests of both co-primary endpoints are significant (i.e., both p-values are ≤ 0.05), then the secondary endpoints will be tested hierarchically at the $\alpha=0.05$ level in the order shown in the Secondary Endpoints section, using the efficacy analysis set. Thus, a secondary endpoint will be tested only if the preceding secondary endpoint in the hierarchy is determined to be significant (i.e., p-value ≤ 0.05). The same statistics will be presented as those for the co-primary endpoints.

For endpoints based on a single time point, such as phonophobia freedom at 2 hours postdose, subjects with missing data at a single time point will also be classified as failures. For endpoints based on multiple time points, such as sustained pain relief from 2 to 48 hours postdose, subjects with missing data at (1) 2, 24, or 48 hours postdose, or (2) more than 1 time point from 3 to 8 hours postdose will also be classified as failures.

9.3.2 *Safety Analyses*

Deaths will be listed without regard to onset for the enrolled analysis set.

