5 SAMPLE SIZE, POWER, AND TYPE 1 ERROR

It is anticipated that about 90% of the 700 subjects randomized to each treatment group will have a headache in the allotted time period, resulting in approximately 630 subjects evaluable for efficacy in each treatment group.

The sample size calculation is based on results from the Phase 2/3 dose-ranging study BHV3500-201. The response rates for the pooled zavegepant 10 mg and 20 mg groups, and for the placebo group in study BHV3500-201 were 22.8% and 15.5%, respectively, for pain freedom at 2 hours postdose, and 42.2% and 33.7%, respectively, for MBS freedom at 2 hours postdose.

A total sample size of 1,260 evaluable subjects (630 per treatment group) provides approximately 91% power for the co-primary endpoint of pain freedom at 2 hours postdose, approximately 88% power for the co-primary endpoint of MBS freedom at 2 hours postdose, and approximately 80% power to detect a difference between treatment groups for both endpoints jointly.

Type I error is controlled by a hierarchical gate-keeping procedure. First, the family of 2 co-primary endpoints is tested. In particular, zavegepant is tested for superiority against placebo at an alpha=0.05 level for both co-primary endpoints. If the tests of both co-primary endpoints are significant (i.e., both p-values are ≤ 0.05), then the secondary endpoints are tested hierarchically at the alpha=0.05 level in the order shown in the Section 3.1.2, using the efficacy analysis set. Thus, a secondary endpoint is tested only if the preceding secondary endpoint in the hierarchy is determined to be significant (i.e., p-value ≤ 0.05). If a test in the hierarchy is not significant, then any further tests on endpoints in the sequence have p-values presented only for descriptive purposes, and no conclusions are drawn from those results.

For exploratory endpoints, no attempt is made to adjust for multiplicity. Any exploratory endpoints for which p-values are produced are evaluated at an unadjusted, 2-sided alpha=0.05 level and presented only for descriptive purposes.

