6.3 Efficacy

Efficacy analyses are based on the efficacy analysis set by as-randomized treatment group only (excluding overall).

Treatment comparisons of binary endpoints are stratified by IWRS prophylactic migraine medication use at randomization except within subgroups. If a single cell has sparse data (< 5 subjects), then the analysis is performed pooled across strata.

All CIs are 2-sided. In treatment comparisons of binary endpoints, CIs are based on a normal approximation to the binomial distribution using asymptotic standard error (ASE). In descriptive analyses of binary endpoints, exact Clopper-Pearson CIs are used. Otherwise, CIs for continuous endpoints are based on the normal distribution.

Postdose efficacy data are slotted into analysis windows automatically by the eDiary (see Section 7.5.2). All efficacy endpoints are assessed using analysis windows, unless specified otherwise.

Methods of handling missing data in analyses of binary efficacy endpoints are defined as follows:

- Non-Completer = Failure (NC=F): Subjects with missing data at a single time point are classified as failures. This missing data imputation method is applied to endpoints based on data from a single time point (e.g., co-primary endpoints) as the main analysis method.
- Non-Completer with Missing Data at More than 1 Time Point = Failure (NC1=F): Subjects with missing data at > 1 time point postdose in a specified time period are classified as failures. This missing data imputation method is applied to endpoints that are based on data

from multiple time points (e.g., secondary endpoint of sustained pain freedom from 2 to 24 hours postdose) as the main analysis method.

- Non-Completer = Missing (NC=M): Subjects with missing data at a single time point are excluded from the analysis. This missing data exclusion method is applied to endpoints based on data from a single time point (e.g., co-primary endpoints) as a sensitivity analysis.
- Multiple imputation (see Section 6.3.2.1). This missing data exclusion method is applied only to the co-primary endpoints as a sensitivity analysis.
- Varying response rate imputation (see Section 6.3.2.1). This missing data exclusion method is applied only to the co-primary endpoints as a sensitivity analysis.

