Treatment group comparisons of the percentage of subjects with sustained pain freedom from 2 to 48 hours postdose use analogous methods as the main analysis of the co-primary endpoint of pain freedom with NC=F, NC1=F, and RM=F (see Section 6.3.2.1).

6.3.3.7 *Freedom from Photophobia, Phonophobia or Nausea at 2 Hours Postdose*

Freedom from each symptom (nausea, phonophobia, photophobia) at 2 hours postdose is assessed separately. Symptom status is measured as present or absent for each symptom (nausea, phonophobia, photophobia).

Symptom freedom at a single time point postdose is defined as a symptom absent at that time point for subjects with the symptom present at the time of dosing. Thus, all analyses of symptom freedom are based on the efficacy analysis set with the symptom present at the time of dosing (see Section 7.5.2), e.g., nausea freedom at a single time point postdose are based on subjects with nausea present at the time of dosing.

Symptom freedom outcomes at 2 hours postdose are tabulated by treatment group (see Section 6.3.4.1).

Treatment group comparisons of the percentage of subjects with symptom freedom at 2 hours postdose use analogous methods as the main analysis of the co-primary endpoint of pain freedom with NC=F and RM=F (see Section 6.3.2.1).

6.3.3.8 *Rescue Medication Use within 24 Hours Postdose*

Analyses are based on the evaluable efficacy analysis set, i.e., subjects in the efficacy analysis set with rescue medication start date on or before study drug start date + 1 day and missing rescue medication start time are excluded. Time to rescue medication use is measured from the study drug start date/time to the rescue medication start date/time.

No analysis window around the 24-hour postdose time point is used.

Rescue Medication Use within 24 Hours Postdose

Rescue medication use within 24 hours postdose is defined as time to rescue medication use ≤ 24 hours.

Treatment group comparisons of the percentage of subjects using rescue medication within 24 hours postdose use analogous methods as the main analysis of the co-primary endpoint of pain freedom, except that the NC=F and RM=F methods are not applied because they are not applicable to this endpoint (see Section 6.3.2.1).

Time to Rescue Medication Use through 24 Hours Postdose

Time to rescue medication use through 24 hours postdose is assessed by treatment group as follows:

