7.5.2 Migraine Characteristics

The following migraine characteristics are collected on study (i.e., on or after the randomization date) (1) before or at the time of dosing in the eDiary Migraine Report and (2) postdose from 15 minutes through 48 hours (e.g., 15, 30, 45, 60, and 90 minutes; 2, 3, 4, 6, 8, 24 and 48 hours) in the eDiary Postdose Migraine Report:

- Pain intensity (none, mild, moderate, severe)
- MBS (nausea, phonophobia, photophobia) before dosing in the eDiary Migraine Report only
- Nausea status (present, absent)
- Nausea intensity (mild, moderate, severe), if nausea status is present
- Phonophobia status (present, absent)
- Phonophobia intensity (mild, moderate, severe), if phonophobia status is present
- Photophobia status (present, absent)

- Photophobia intensity (mild, moderate, severe), if photophobia status is present
- Functional disability level (normal, mildly impaired, severely impaired, requires bedrest)
- Aura (yes, no) preceding or accompanying headache before dosing in the eDiary Migraine Report only.

The eDiary allows subjects to report one result per time point per migraine characteristics parameter.

In general, if subjects answered “no” to taking study medication mistakenly already, had current pain intensity of moderate or severe before dosing, and did not use other headache medications, then the eDiary Migraine Report collects current levels of all parameters on study before dosing and at scheduled postdose time points.

Otherwise, if subjects answered “yes” to taking study medication mistakenly already and provided the time of study medication taken, then the eDiary Migraine Report collects all parameters listed above (1) retrospectively at the time of dosing except MBS and aura, and (2) prospectively at scheduled postdose time points (as applicable based on study medication time).

For analyses, migraine characteristics collected in the eDiary Migraine Report are considered to be “at the time of dosing”, except MBS and aura, which is considered to be “on study before dosing”.

Windows for postdose efficacy measurements (15, 30, 45, 60, 90 minutes; 2, 3, 4, 6, 8, 24, and 48 hours) are automatically assigned by the eDiary as shown in [Table 5](#).

Table 5: eDiary Automated Efficacy Analysis Windows

Postdose Evaluation	Analysis-Specified Interval	Target Time
15 minutes	10 to 20 minutes	Study medication start time + 15 minutes
30 minutes	25 to 35 minutes	Study medication start time + 30 minutes

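### Optional precision gain: symptom intensity at dosing is recorded but not used in the tests of phonophobia, photophobia, nausea or MBS freedom

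*Protocol*

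**What the plan says.** **What is recorded.** Protocol 6.4.2 asks for presence or absence of nausea, phonophobia and photophobia, and adds: "In addition, subjects will record the intensity of the symptom on a 4-point numeric rating scale (none, mild, moderate, or severe) in the handheld". SAP 7.5.2 lists the graded item for each symptom, at dosing and postdose, for example "Phonophobia intensity (mild, moderate, severe), if phonophobia status is present". SAP 6.2.5.2 equates an intensity of none with an absent symptom, so the four-level and three-level descriptions agree.

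**Where it is used.** SAP 6.2.5.2 tabulates intensity at dosing as a migraine characteristic.

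**How the tests are built.** Protocol 9.3.1.1 specifies a Cochran-Mantel-Haenszel (CMH) comparison "stratified by prophylactic migraine medication use at randomization (yes or no"). SAP 6.3 applies that single factor to all binary treatment comparisons outside subgroups, and SAP 6.3.2.2 repeats it for MBS freedom. For the three symptoms, SAP 6.3.3.7 takes over the pain freedom method ("percentage of subjects with symptom freedom at 2 hours postdose use analogous methods as the main analysis of the co-primary endpoint"), restricted to subjects who had the symptom at dosing. Symptom intensity is not a stratum, a listed subgroup (SAP 4.3) or a listed covariate for multiple imputation (SAP 6.3.2.1). That last list does include headache pain intensity at dosing.

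**Sparse data.** SAP 6.3 drops stratification and pools when a single cell holds fewer than 5 subjects.

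**The concern.** Everyone analysed for endpoints 7, 8 and 16 has the symptom at dosing, so baseline status is constant. Graded intensity is then the only recorded baseline information on that symptom that still varies. The planned test treats a subject whose phonophobia was mild at dosing like one whose phonophobia was severe. If intensity predicts freedom at 2 hours, stratifying on it would narrow the interval and remove chance imbalance in severity between arms.

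Two features of the plan give this some weight. MBS freedom has the lower stated power of the two co-primaries (about 88%), and both must succeed. Secondary endpoints are tested in a fixed order, so a miss at endpoint 7 or 8 leaves all later endpoints descriptive. The symptom endpoints are also tested in subsets of the planned sample.

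**Working it through.** **Inputs from the documents.** "A total sample size of 1,260 evaluable subjects (630 per group"), 1:1 allocation (Protocol 5.1). MBS freedom 42.2% v 33.7% and pain freedom 22.8% v 15.5% (Protocol 9.1). In SAP 5, "zavegepant is tested for superiority against placebo at an alpha=0.05 level for both co-primary endpoints". SAP 6.3 states "All CIs are 2-sided"; the co-primary tests are taken as two-sided too.

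**1. The plan's own power.** SE = √{[p₁(1−p₁) + p₀(1−p₀)]/n}; power = Φ(difference/SE − 1.96).

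- Pain freedom: √(0.3070/630) = 0.02207; 0.073/0.02207 = 3.307; power 91.1% (stated about 91%).
- MBS freedom: √(0.4673/630) = 0.02724; 0.085/0.02724 = 3.121; power 87.7% (stated about 88%).
- Joint, as the product: 0.911 × 0.877 = 79.9% (stated about 80%).

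The pooled-variance formula gives 91.0%, 87.6% and 79.6%. A one-sided 0.05 test would give 95.1% and 92.9%, which do not match, so the two-sided reading is right.

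**2. Effect of stratifying by intensity.** The documents give no intensity distribution, no response by intensity and no symptom-subset sizes. Assumed:

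- mild/moderate/severe split of 25/50/25%;
- MBS planning rates overall, with a constant odds ratio (OR) per intensity step, solved so that the weighted rates average 42.2% and 33.7%;
- symptom subsets of 440 or 380 per arm, with the same rates.

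Stratified variance = Σ w[p₁(1−p₁) + p₀(1−p₀)]/n.

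| OR per step | Placebo rate, mild / moderate / severe | Σ term | Variance reduction | Power, n=630 (MBS) | n=440 | n=380 |
|---|---|---|---|---|---|---|
| 1 | 33.7 / 33.7 / 33.7% | 0.4673 | 0 | 87.7% | 74.2% | 67.9% |
| 1.5 | 42.9 / 33.4 / 25.1% | 0.4586 | 1.9% | 88.3% | 75.0% | 68.7% |
| 2 | 49.5 / 32.8 / 19.7% | 0.4429 | 5.2% | 89.4% | 76.4% | 70.2% |
| 3 | 58.1 / 31.6 / 13.4% | 0.4120 | 11.8% | 91.4% | 79.3% | 73.3% |

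Example, OR 2 and n=630: SE = √(0.4429/630) = 0.02652; 0.085/0.02652 = 3.206; power = Φ(1.246) = 89.4%. Joint power moves from 79.9% to 80.4%, 81.4% and 83.2%.

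**3. Check by simulation.** 6,000 trials per scenario, 630 per arm, 15% on prophylaxis (assumed), same intensity split. CMH by prophylaxis alone was compared with CMH by prophylaxis × intensity, for a response gradient in percentage points per intensity step.

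| Gradient | Variance ratio | Power without → with intensity |
|---|---|---|
| 0 | 1.01 | 87.4% → 87.2% |
| 10 | 0.98 | 87.8% → 88.4% |
| 15 | 0.95 | 87.3% → 88.5% |
| 20 | 0.91 | 88.3% → 90.7% |

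**4. Sparse-cell rule.** With the same assumed 15% on prophylaxis, the severe stratum on prophylaxis holds about 630 × 0.15 × 0.25 = 24 subjects per arm. If a cell means subjects by arm, the rule does not bite. If it means responders by arm, the expected placebo count is 24 × 0.197 ≈ 4.7 at OR 2 and 24 × 0.134 ≈ 3.2 at OR 3. Both are below 5, so the whole analysis would be pooled. A small extra level for missing values would make this more likely. The rule therefore has to be handled in any change.

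**The case against.** **The plan is not defective.** Stratifying by the single randomization factor is standard, the tests are valid, and the planned power is reached without further adjustment. This stands in full. A reader might infer that the tests are biased or the trial underpowered because intensity is left out; the documents support neither.

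**The benefit is unproven.** No document gives response by intensity. The largest gain needs an odds ratio of 3 per step, meaning placebo MBS freedom of about 58% if mild and 13% if severe. This also stands: only the direction can be argued, and only if intensity is prognostic. That headache pain intensity is a possible imputation covariate suggests the sponsor thinks severity may matter, but says nothing about the size for symptoms.

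**The gating argument can be overdrawn.** Any of endpoints 1 to 16 blocks those below it. Endpoints 7 and 8 are not special, and endpoint 16 gates only endpoint 17.

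**A careless change could do harm.** Separate levels for missing MBS, or for subjects who dosed before using the eDiary, could be small enough to trigger pooling and lose even the present stratification. Subjects with no predose MBS are failures by definition (SAP 6.3.2.2), so a stratum made only of them has no responders. Changing the SAP without Protocol 9.3.1.1 would make the two documents disagree on a co-primary test. Leaving SAP 6.3.4.4 alone would give a second p-value for the same 2-hour comparison. These points shape the fix; they do not remove the case for it.

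**Conclusion.** The omission is real: intensity at dosing is collected and tabulated, and none of the four tests uses it. It is a missed efficiency of low priority, not an error.

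Under assumed odds ratios of 1.5 to 2 per intensity step, the variance falls by about 2% to 5% and MBS power rises by about 0.6 to 1.7 points. At an odds ratio of 3 the figures are about 12% and 3.7 points. In the assumed symptom subsets the gain is about 1 to 5 points. With no association the loss is negligible. All of these rest on the assumed intensity split and gradients, and the subset figures also on assumed sizes and MBS-like rates.

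It would overstate the point to call intensity the baseline of the outcome itself. The outcome is presence or absence; intensity is a three-level covariate closely related to it.

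**What to change.** Before unblinding:

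1. **Endpoints 7, 8 and 16.** Amend SAP 6.3 and 6.3.3.7 and Protocol 9.3.1.2 to stratify by IWRS prophylactic use and by that symptom's intensity at dosing (mild, moderate, severe).
2. **Sparse cells.** State in SAP 6.3 what a cell is. When one has fewer than 5 subjects, merge adjacent intensity levels first, and pool across all strata only as a last resort.
3. **Retrospective or missing values.** Use intensity reported retrospectively (SAP 7.5.2) as recorded. Merge missing intensity into a pre-specified level instead of forming a small stratum.
4. **MBS freedom, if included.** Use the intensity of the symptom named as MBS, under the same merging rule. Place missing MBS, or an intensity of none, in a pre-specified level. Amend SAP 6.3.2.2 and Protocol 9.3.1.1 together.
5. **Consistency.** Align the 2-hour comparisons in SAP 6.3.4.4 and keep the current analysis as supportive.

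The cost is wording in both documents and one variable already in the eDiary; no new data are needed. The downside is more strata (up to 6 instead of 2) and a slightly more complex analysis. If MBS freedom is changed, the two co-primaries will also have different strata.
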